##### **Biomarker Efficacy:**

---

1. a2AP activity at 3 ( $\pm 1$ ) h after completion of study drug administration
2. Matrix metalloproteinase-9 plasma level 3 ( $\pm 1$ ) h after completion of study drug administration.
3. % tissue reperfusion on perfusion scan obtained at 30 ( $\pm 4$ ) h after study drug administration compared to the baseline

#### **Pharmacokinetics and anti-drug antibodies:**

1. PK profile of TS23 at 3 ( $\pm 1$ ) h, and 30 ( $\pm 4$ ) h, and 90 ( $\pm 7$ ) days, after completion of study drug administration.
2. Evaluation of anti-drug antibodies to TS23 (at baseline and 90 ( $\pm 7$ ) days follow-up visit).

#### **Safety:**

1. Incidence of symptomatic ICH within 30 ( $\pm 4$ ) h of study drug administration (SITS-MOST definition) ([Wahlgren, Ahmed et al. 2007](#))
2. Incidence of non-ICH major or clinically relevant non-major bleeding within 30 days of study drug administration.
3. Non-bleeding, SAEs within 90 ( $\pm 7$ ) days
4. Incidence of stroke-related and all-cause deaths within 90 ( $\pm 7$ ) days
5. Plasma fibrinogen levels at 3 ( $\pm 1$ ) h after completion of TS23 therapy

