**Clinical Efficacy:**

1. Improvement in level of global disability (Modified Rankin Scale (mRS) distribution) at 90 ( $\pm 7$ ) days.
  2. Frequency of excellent functional outcome (mRS 0-1) at 90 ( $\pm 7$ ) days.
  3. National Institutes of Health Stroke Scale (NIHSS) at 72 ( $\pm 12$ ) h (or discharge if sooner; adjusted for the baseline in analysis)
-

Pharmacokinetics and anti-drug antibodies:

1. Pharmacokinetic (PK) profile of TS23 at 3 (+/-1) h and 30 ( $\pm$ 4) h after completion of therapy and 90 ( $\pm$ 7) days.
2. Evaluation of anti-drug antibodies to TS23 (at baseline and 90 ( $\pm$ 7) d follow-up visit).

Safety:

1. Incidence of symptomatic ICH within 30 ( $\pm$ 6) h of study drug administration [SITS-MOST definition (a local or remote type II parenchymal hemorrhage within 30 ( $\pm$ 4) h after treatment associated with a  $\geq$  4-point deterioration on the NIHSS score from baseline or from the lowest score from baseline to 24 hours, or leading to death.)]
2. Incidence of non-ICH major or clinically relevant non-major bleeding within 30 days of study drug administration.
3. Non-bleeding, serious adverse events (SAEs) within 90 ( $\pm$ 7) days
4. Incidence of stroke-related and all-cause deaths within 90 ( $\pm$ 7) days
5. Plasma fibrinogen levels at 3 (+/-1) h after completion of study drug administration

**Study Population:** We will enroll a total of 300 adults ( $\geq$ 18 years) with acute ischemic stroke who have a baseline NIHSS  $\geq$ 6 and are able to receive study drug within 4.5-24 hours after stroke onset (or last known well) who have evidence of core-penumbra mismatch on baseline perfusion imaging and are not planned for endovascular intervention or standard of care intravenous (IV) thrombolysis.

**Phase:** 2

**Description of Sites/Facilities Enrolling Participants:** Consecutive eligible patients will be screened and enrolled in up to 50 comprehensive stroke centers in the U.S. Currently, no sites outside of the U.S. are planned.

**Description of Study Intervention:** The study intervention arms are TS23 (dosed at 3, 5, 7, or 10 mg/kg) or matching placebo. Study drug is administered intravenously as

[figure not shown]

short IV infusion after reconstitution over ~15 minutes (max dose of 1000 mg).

**Study Duration:** 54 months

**Participant Duration:** 3 months

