## 9 SAFETY ASSESSMENTS

### 9.1 Primary safety endpoint

ANY ICH visualized on the 30 ( $\pm 4$ ) h CT scan is the primary study endpoint for SISTER. This will be determined on the 30 ( $\pm 4$ ) h CT scan uploaded in the central imaging databank by local study personnel, by a trained neuroradiologist who is blinded to the participant's study group assignment.

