### 9.2 Secondary safety endpoints

1. Incidence of symptomatic ICH within 30 ( $\pm 4$ ) h of study drug administration (SITS-MOST definition). ([Wahlgren, Ahmed et al. 2007](#)) The presence of type-2 parenchymal hematoma will be determined by a central, blinded, neuroradiologist and a worsening in NIHSS will be determined by the NIHSS reported on the study CRF by the local, certified, blinded assessors.
2. Incidence of non-ICH major or clinically relevant non-major bleeding within 30 days of study drug administration.

Non-ICH major bleeding is defined as clinically overt bleeding, that is not ICH, with one or more of the following:

- causing a fall in hemoglobin of 2 g/dL or more,
  - or leading to a transfusion of 2 or more units of packed red blood cells or whole blood,
-

- symptomatic and occurring in a critical site: intracranial, intraspinal, intraocular, pericardial, intra- articular, intramuscular with compartment syndrome, retroperitoneal,
- contributing to death.

Clinically relevant non-major (CRNM) bleeding is defined as overt bleeding not meeting the criteria for major bleeding that requires medical attention or is associated with discomfort for the subject such as pain, or impairment of activities of daily life.

All other overt bleeding episodes not meeting the criteria for major or CRNM bleeding will be classified as nuisance bleeding.

Symptomatic ICH, non-ICH major bleeding, and CRNM will be adjudicated by the study independent medical monitor (IMM)

3. Non-bleeding, SAEs within 90 ( $\pm 7$ ) days will be determined by direct interview during all study visits.
4. Incidence of stroke-related and all-cause deaths within 90 ( $\pm 7$ ) days will be determined by direct interview.
5. Plasma fibrinogen levels at 3 (+/-1) h after completion of TS23 therapy will be determined by laboratory testing of study-specific blood draw.

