### **9.3.4 Time Period and Frequency for Event Assessment and Follow-Up**

The occurrence of an AE or SAE may come to the attention of study personnel during study visits and interviews of a study participant presenting for medical care, or upon review by a study monitor.

All AEs including local and systemic reactions not meeting the criteria for SAEs will be captured on the appropriate CRF. Information to be collected includes event description, time of onset, clinician's assessment of severity, relationship to study product (assessed only by those with the training and authority to make a diagnosis), and time of resolution/stabilization of the event. All AEs occurring while on study must be documented appropriately regardless of relationship. All AEs will be followed to adequate resolution.

Any medical condition that is present at the time that the participant is screened will be considered as baseline and not reported as an AE. However, if the study participant's condition deteriorates at any time during the study, it will be recorded as an AE.

Changes in the severity of an AE will be documented to allow an assessment of the duration of the event at each level of severity to be performed. AEs characterized as intermittent require documentation of onset and duration of each episode.

The study coordinator will record all reportable events with start dates occurring any time after informed consent is obtained until the patient completes their 90-day visit. At each study visit, the investigator will inquire about the occurrence of AE/SAEs since the last visit. Events will be followed for outcome information until resolution or stabilization.

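### Non-fatal serious non-intracranial bleeding on days 31 to 90, and non-fatal serious ICH first arising after the 30-hour window, are counted in none of the listed safety endpoints

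*Protocol*

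**What the plan says.** The secondary safety endpoints appear three times in the protocol: in the synopsis (1.1), in section 3.2 and in section 9.2. On the points that matter here the three statements agree.

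- Endpoint 2 is "Incidence of non-ICH major or clinically relevant non-major bleeding within 30 days of study drug administration".
- Endpoint 3 reads "Non-bleeding, serious adverse events (SAEs) within 90" (±7) days in the synopsis and "Non-bleeding, SAEs within 90" (±7) days in section 3.2. Section 9.2 keeps the non-bleeding restriction and adds how events are found: "days will be determined by direct interview during all study visits".
- Endpoint 4 is "Incidence of stroke-related and all-cause deaths within 90" (±7) days. It does not exclude deaths from bleeding.
- Endpoint 1 begins "Incidence of symptomatic ICH within 30" (±4) h, and the primary safety endpoint is "ANY ICH visualized on the 30" (±4) h CT scan (section 9.1).
- Endpoint 5 is plasma fibrinogen at 3 (±1) h.

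Collection is wider than the endpoint list. Section 9.3.4 records reportable events of any type from consent "until the patient completes their 90-day visit". Section 9.5 has the independent medical monitor review every SAE, with no exception for bleeding. The protocol gives no reason for the 30-day limit on endpoint 2 or for the non-bleeding restriction on endpoint 3.

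**The concern.** Keeping bleeding apart from other SAEs is sensible when the two endpoints cover the same period, because it avoids double counting. Here one runs to day 30 and the other to day 90. A serious bleed after day 30 is too late for endpoint 2 and of the wrong type for endpoint 3. A non-fatal retroperitoneal bleed on day 45, for example, would be recorded as an SAE and would appear in no listed safety endpoint.

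What is at stake is whether the 90-day SAE endpoint gives a complete count by dose. Section 6.1.1 names bleeding as the adverse event most to be expected with TS23. It also says that the risk may be higher with concomitant antithrombotics. Section 8.5 lists standard antithrombotics started by the end of day 2, so many participants may be taking them during days 31 to 90. Human experience before this trial is four cohorts of six healthy volunteers (section 2.4).

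**Working it through.** The protocol states no figure that could be reproduced on this point. The check sets each safety endpoint against type of event and time.

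| Endpoint | Events admitted | Window | Non-fatal serious non-ICH bleed, days 31–90 | Non-fatal serious ICH first arising after the 30 (±4) h window |
|---|---|---|---|---|
| Primary safety | Any ICH on CT | 30 (±4) h | No: not ICH | No: window over |
| Secondary 1 | Symptomatic ICH (SITS-MOST) | 30 (±4) h | No: not ICH | No: window over |
| Secondary 2 | Non-ICH major or clinically relevant non-major bleeding | Day 30 | No: window over | No: ICH excluded |
| Secondary 3 | Non-bleeding SAEs | Day 90 (±7) | No: bleeding excluded | No: bleeding excluded |
| Secondary 4 | Deaths | Day 90 (±7) | No: not fatal | No: not fatal |
| Secondary 5 | Fibrinogen | 3 (±1) h | No | No |

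Both right-hand columns are empty of any endpoint that counts the event. If the bleed is fatal, endpoint 4 counts it as a death, though not as a bleed.

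**Length of the gap, non-ICH bleeding.** Inputs: day 30 (endpoint 2) and day 90 ±7 (endpoint 3).
- Nominal: 90 − 30 = 60 days, and 60/90 = 67% of follow-up.
- With the visit window: 83 − 30 = 53 days to 97 − 30 = 67 days.

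**Length of the gap, ICH.** The window closes at the latest at 30 + 4 = 34 h, or 34/24 = 1.4 days. To day 90 that leaves 90 − 1.4 = 88.6 days. The synopsis once prints ±6 h for symptomatic ICH, which would move the start to 36 h (1.5 days) and change nothing of substance.

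**One ambiguity on ICH.** The definition of major bleeding in section 9.2 excludes ICH in its opening words but then lists intracranial among the critical sites. If the list prevailed, a symptomatic intracranial bleed up to day 30 could enter endpoint 2, and the ICH gap would then start at day 31. The endpoint's title and the opening words of the definition both say non-ICH, so the table follows them.

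**Illustrative count.** The protocol gives no rate for late serious bleeding. Assume that 1 to 3% of the 300 participants have a non-fatal serious non-ICH bleed on days 31 to 90:
- 0.01 × 300 = 3, and 0.03 × 300 = 9.
- Averaged over five groups: 3/5 = 0.6 to 9/5 = 1.8 per group.

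This shows scale only and is not an estimate.

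**The case against.** The strongest reply is that the three statements of the endpoints agree, so nothing is contradictory, and that a 30-day bleeding window after a single infusion of about 15 minutes is a defensible choice. That stands, and the fix leaves the window alone. It does not explain why the 90-day SAE endpoint should then exclude bleeding.

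Several stronger readings are tempting, and the documents do not support them:

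- *That late serious bleeding is missed altogether.* Fatal bleeds are counted in endpoint 4, and all events are recorded to the 90-day visit (9.3.4).
- *That safety oversight is blind to these events.* The medical monitor reviews all SAEs. The semi-annual DSMB reports cover the most frequent and most serious adverse events, and the closed report is by partially blinded group (9.5). None of this excludes bleeding.
- *That a trial decision is affected.* Success rests on the utility built from early ICH and NIHSS, and the safety stopping probability uses the ICH rate (10.2).
- *That the final report will omit these bleeds by dose.* Full SAE tables may be specified in the SAP, which is not at hand. The claim is limited to the endpoints listed in the protocol.
- *That a late drug effect would be hidden.* Section 2.4 describes a2AP inhibition above about 50% as lasting hours to 4 days at 2.5 to 7.5 mg/kg, so any drug contribution after day 30 is probably small. No duration is given there for 10 mg/kg. The 67% is calendar time, not time at drug-related risk.

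At an average of roughly one or two events per group, in patients who may be on antithrombotics, the late extracranial count would also say little about dose. The ICH half of the gap begins much nearer to exposure and is the more relevant to the drug.

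**Conclusion.** The point holds as a gap in endpoint definition and reporting, not in data capture or oversight. As worded, non-fatal serious non-intracranial bleeding on days 31 to 90 (nominally 60 of 90 days) and non-fatal serious ICH first arising after the 30 (±4) h window are collected but enter no listed safety endpoint. Fatal bleeding in those periods is counted only as a death. This follows from the wording in sections 1.1, 3.2 and 9.2 and needs no numerical assumption. The ICH part takes the non-ICH title of endpoint 2 at its word. The figure of 3 to 9 events depends wholly on the assumed 1 to 3% rate and should be read as an illustration. The priority is minor, and the correction is worth making because it costs almost nothing.

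**What to change.** In sections 1.1, 3.2 and 9.2, reword safety endpoint 3 as: *All SAEs within 90 (±7) days, with bleeding (intracranial and non-intracranial) and non-bleeding SAEs shown separately by dose.* Leave endpoints 1 and 2 unchanged.

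Some serious bleeds up to day 30 will then appear both in endpoint 2 and in the bleeding part of endpoint 3. The separate display makes that overlap visible, and the non-bleeding count remains available.

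Extending endpoint 2 to day 90 instead would close only the non-ICH part. Removing the restriction from endpoint 3 closes both.

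The cost is a wording change in three places. SAEs are already collected to the 90-day visit and already reviewed by the medical monitor, so no visit, data item, sample size or decision rule changes.

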### **3.3 Rationale and assessment of endpoints**

**NIHSS:** We choose 30 ( $\pm 4$ ) h NIHSS (adjusted by baseline NIHSS) as our primary efficacy outcome measure as an ideal combination of good surrogate properties, feasibility, and strong biological rationale. NIHSS is a common surrogate marker for early-phase stroke trials ([Lyden, Lu et al. 2001](#), [Saver, Goyal et al. 2015](#), [Lapergue, Blanc et al. 2017](#), [Goldstein, Lennihan et al. 2018](#)) and, when analyzed appropriately using regression methods, ([Young, Weir et al. 2005](#), [Meyer, Broocks et al. 2020](#), [Mistry, Yeatts et al. 2020](#), [Mistry, Yeatts et al. 2021](#)) is strongly associated with patient-centered outcomes, including the 90d mRS global disability scale. A 72-hour NIHSS will be measured as a key secondary outcome to capture the prolonged neurological effects of TS23 in the subacute period. To minimize bias, the NIHSS will be assessed by a certified rater who will be blinded to the patients' study group assignment.

**Any ICH:** We choose ANY ICH to evaluate the safety of TS23 more robustly, as opposed to the commonly used symptomatic ICH outcome. In recent studies, ANY ICH is shown to be associated with worse 90-day global disability outcomes. ([Gay, Collie et al.](#)) In fact, we account for this safety outcome in our sample size and power calculations and are well-positioned to readily detect safety

---

issues with TS23. EXTEND trial data in the non-LVO subset (personal communication, [name]) and data pooled from other major thrombolytic trials (Lees, Bluhmki et al. 2010) informed our assumptions.

**mRS** analyzed as ordinal global disability scale and dichotomous excellent outcome (mRS 0-1): mRS is the most commonly used, patient-reported, functional disability outcome in acute stroke trials. (Lees, Bath et al. 2012, Lees, Khatri et al. 2016) To increase outcome comparability and minimize bias, the modified Rankin Scale assessments of global disability will be obtained at all sites using the formal, algorithmic Rankin Focused Assessment-Ambulatory (RFA-A) method by trained raters. (Saver, Filip et al. 2010)

**a2AP and MMP-9 level at 3(+/-1)-hour after completion of therapy:** TS23 mechanistically lowers a2AP activity by binding to the a2AP molecule to prevent it from inhibiting plasmin. It also lowers the MMP-9 activity, which is a biomarker linked to stroke severity, as noted above in pre-clinical and phase-1 human studies. We will measure the levels of a2AP and MMP-9 in the blood of patients who receive study drug and placebo to establish mechanistic efficacy in AIS patients via a study-specific lab draw.

**Tissue reperfusion:** An attractive property of TS23, that stands in favorable distinction from plasminogen activators, is that it reduces micro thrombosis and thus improves tissue reperfusion, which we will measure on the 30 ( $\pm 4$ ) h follow-up CT or MR perfusion scan and calculate the percentage of the baseline hypo perfused tissue (volume of  $T_{max} > 6s$ ) that remains hypo-perfused at 30 ( $\pm 4$ ) h. A study-specific perfusion scan, using the same perfusion modality that was used at baseline, will be performed at 30 ( $\pm 4$ ) h after study drug infusion.

Symptomatic ICH and non-ICH major or clinically relevant non-major bleeding events are the most feared complications of thrombolytic medications. For SISTER, the symptomatic ICH will be defined using the SITS-MOST definition (Wahlgren, Ahmed et al. 2007) and other major or clinically relevant non-major bleeding events will be determined by the local study investigators as detailed in the protocol Section 9.

## 4 STUDY DESIGN

### 4.1 Overall Design

SISTER is a Phase IIa, Bayesian, adaptive, randomized dose-finding trial of TS23 in patients with acute ischemic stroke. The study will randomize to 4 doses of TS23 (3, 5, 7, 10 mg/kg) and placebo. The trial will randomize and initiate study medication for 300 subjects. The first 50 subjects will be randomized in a dose escalation burn-in period, allocating 10 subjects to each group starting with the lowest dose. Response Adaptive Randomization updates will occur every 50 subjects, thereafter, (favoring doses with maximum utility). For each block of 50 subjects, 13 are allocated to control. The trial may stop early for safety.

Up to 50 sites are planned for the trial. We hypothesize that TS23 will be safe and potentially more efficacious than placebo for the enrolled group of patients.

---

## 4.2 Scientific Rationale for Study Design

TS23 is a novel molecule and the SISTER trial is testing this novel thrombolytic in patients with acute ischemic stroke for the first time. The best dose of TS23 for these patients is unknown. Pre-clinical studies have shown that TS23 works without increasing safety concerns. We will test TS23 alone against placebo and determine the dose of TS23 that has the best combination of safety (measured as any ICH on CT brain) and efficacy (measured on the NIHSS). By enrolling concurrently placebo-treated patients, we will be well-positioned to compare all TS23 arms against placebo in the final analysis.

## 4.3 Justification for Dose

The Phase II SISTER Trial seeks to identify the optimal dose of TS23 that is safest and most effective at reducing neurological deficits in ischemic stroke vs. control. The doses chosen in this study (3, 5, 7 and 10 mg/kg up to a max of 1000 mg) are within the range of TS23 dosing that was shown to be safe in phase-I human studies (2.5-10 mg/kg; as noted above). Since thrombus dissolution increases significantly when a2AP levels are less than ~50%, we selected a dose range of TS23 (3-10 mg/kg) that inhibits a2AP activity by ~50% to >95%.

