#### **Dosage and Administration**

TS23 will be administered as a ~15-minute IV infusion at the dose stipulated in study protocols. In the phase 1 study (TS CP01-2015) in healthy participants, TS23 was administered as single IV infusion dose ranging from 2.5 mg/kg to 10.0 mg/kg.

---

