## **Special Populations**

TS23 has not yet been tested in children, adults over 60 years of age, or participants with renal or hepatic impairment.

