### **Overdose**

All attempts will be made to minimize overdosing by providing a simple dosing table to all sites ([Table 2](#)). There is currently no information available regarding potential overdose of TS23. In case of suspected overdose, participants should be closely monitored in an inpatient, supervised setting. Supportive care measures should be initiated as determined by the investigator's judgment. Due to the known mechanism of action of TS23, AEs events associated with TS23 overdose are likely to be related to increased fibrinolysis. In such cases, antifibrinolytic agents such as epsilon amino caproic acid (Amicar) or tranexamic acid (Lysteda) should be considered if clinically indicated and used according to the package inserts.

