### 6.1.2 Dosing and Administration

In the SISTER trial, five different dose cohorts will be studied:

Cohort 1: placebo (for TS23)

Cohort 2: 3.0 mg/kg TS23

Cohort 3: 5.0 mg/kg TS23

Cohort 4: 7.0 mg/kg TS23

Cohort 5: 10.0 mg/kg TS23

The doses will be administered according to the following dosing provided in [Table 2](#).

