**Table 2. Dosing Based on Patient Weight**

| Weight (kg) | TS23 dose mgs |         |         |          |
|-------------|---------------|---------|---------|----------|
|             | 3 mg/kg       | 5 mg/kg | 7 mg/kg | 10 mg/kg |
| <60         | 180           | 300     | 420     | 600      |
| 60 to <70   | 210           | 350     | 490     | 700      |
| 70 to <80   | 240           | 400     | 560     | 800      |
| 80 to <90   | 270           | 450     | 630     | 900      |
| ≥90         | 300           | 500     | 700     | 1000     |

TS23 study drug is provided in 10 ml vials at a concentration of 10 mg/ml. The study drug will be diluted by the study pharmacist with sterile 0.9% saline to a total volume of 200 ml for infusion as described in the Pharmacy Manual. A placebo solution consisting of 200 ml of the diluent (0.9% saline for infusion) will be dosed in a similar manner to maintain the double-blind study design. TS23 diluted for infusion with 0.9% saline and 0.9% saline have a similar appearance. The diluted study drug or placebo will be given to the study team by an unblinded site pharmacist without indication of the identity of the drug, so as to maintain blinding. Participants will either receive the study drug (200 ml) or 0.9% saline placebo (200 ml), which will be given intravenously as a single dose, over an infusion time of about ~15 minutes. At the highest dose of TS23, this corresponds to a maximum rate of  $\leq 0.67$  mg/kg/min.

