### **7 STUDY INTERVENTION DISCONTINUATION AND PARTICIPANT DISCONTINUATION/WITHDRAWAL**

#### **7.1 Discontinuation of Study Intervention**

All patients enrolled in the SISTER trial will be monitored during the study drug administration and for at least 4 hours following the completing of drug administration in high acuity setting (such as the emergency department, intermediate care unit or ICU) for development of adverse reactions and without disruption of the standard clinical care. No dose reductions are allowed in this study. Temporary interruptions in the administration of study drug infusions, other than brief ones to address a blocked IV line, are also not allowed in this study. It is expected that all randomized participants will receive the complete treatment (~15 minutes infusion), unless there is a safety issue that prevents completion of the infusion. If the patient develops hemorrhagic complications or anaphylaxis to the drug administration, the study medication may be halted. In such an event, the patient will be treated for the complications per the local investigators' best judgement.

If there is a need to interrupt administration of the study drug infusion because of a safety concern, then study drug administration must be permanently discontinued. The reason for discontinuation and the amount of dose administered will be documented.

Information regarding the type of reaction leading to discontinuation of study intervention, total duration of administration, total dose administered, and treatment needed for the reaction will be noted

---

on the CRF. The event responsible for study drug discontinuation will be noted as an AE or SAE and/or UP (Please see Section 9 below).

Discontinuation from study intervention does not mean discontinuation from the study, and remaining study procedures should be completed as indicated by the study protocol. If a clinically significant finding is identified (including, but not limited to changes from baseline) after enrollment, the investigator or qualified designee will determine if any change in participant management is needed. Any new clinically relevant finding will be reported as an AE.

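### Table 2 gives every patient under 100 kg in the 10 mg/kg arm more than 10 mg/kg, so the claim in Section 4.3 that all doses lie within the phase 1 range is not true as dosed

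*Protocol*

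**What the plan says.** Section 4.3 introduces the arms with "The doses chosen in this study (3, 5, 7 and 10 mg/kg up to a max of 1000 mg") and states that they "are within the range of TS23 dosing that was shown to be safe in phase-I human studies", which it gives as 2.5-10 mg/kg. Section 2.4 reports the same range, from four cohorts of six healthy volunteers. Section 6.1.1 (Dosage and Administration) repeats it: "TS23 was administered as single IV infusion dose ranging from 2.5 mg/kg to 10.0 mg/kg".

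The dose a patient receives is set in Section 6.1.2: "The doses will be administered according to the following dosing provided in" Table 2. The table fixes one milligram dose per arm for each of five bands: under 60, 60 to under 70, 70 to under 80, 80 to under 90, and 90 kg and over. In the 10 mg/kg column the doses are 600, 700, 800, 900 and 1000 mg. The text under the table adds "At the highest dose of TS23, this corresponds to a maximum rate of" at most 0.67 mg/kg/min, for an infusion of about 15 minutes.

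Section 6.1.1 (Overdose) presents this table as the safeguard: "All attempts will be made to minimize overdosing by providing a simple dosing table to all sites".

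**The concern.** A weight-banded table can round towards the middle of each band, so that errors fall both ways, or to one end. This one appears to round only upwards for anyone below 100 kg. In the three lower arms that shifts the delivered dose but leaves it under 10 mg/kg at ordinary adult weights. In the top arm the label already equals the highest dose that the protocol reports from phase 1, so any upward rounding goes past it.

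The range in Section 4.3 is the protocol's stated safety basis for the doses, and investigators and safety reviewers will read it as a limit on exposure. TS23 is fibrinolytic, and Section 6.1.1 names bleeding as the most commonly anticipated adverse event. The same section says "TS23 has not yet been tested in children, adults over 60 years of age, or participants with renal or hepatic impairment", while Section 5.1 sets no upper age limit and neither 5.1 nor 5.2 sets a minimum weight. The age gap affects all active arms and is not caused by the table, but it leaves less reason to exceed the tested range without saying so. The 1000 mg cap does not help, because it does not limit mg/kg below 100 kg.

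**Working it through.** **Inputs.** Table 2 milligram doses and weight bands (Section 6.1.2); phase 1 maximum of 10 mg/kg (Sections 2.4, 4.3 and 6.1.1); infusion time of about 15 minutes and stated maximum rate of 0.67 mg/kg/min (Section 6.1.2).

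**Step 1: the weight behind each row.** Table dose divided by label, 3 mg/kg column: 180/3 = 60, 210/3 = 70, 240/3 = 80, 270/3 = 90, 300/3 = 100 kg. The 5, 7 and 10 mg/kg columns give the same five weights. Each closed band is dosed at the upper limit that it excludes. The open top band is dosed at 100 kg.

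**Step 2: delivered dose in the 10 mg/kg arm.** Table dose divided by actual weight; rate = delivered mg/kg divided by 15; minutes needed = delivered mg/kg divided by 0.67.

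| Weight (kg) | Dose (mg) | mg/kg | Excess over 10 | mg/kg/min over 15 min | Minutes to meet 0.67 |
|---|---|---|---|---|---|
| 45 | 600 | 13.33 | 33.3% | 0.889 | 19.9 |
| 50 | 600 | 12.00 | 20.0% | 0.800 | 17.9 |
| 60 | 700 | 11.67 | 16.7% | 0.778 | 17.4 |
| 70 | 800 | 11.43 | 14.3% | 0.762 | 17.1 |
| 80 | 900 | 11.25 | 12.5% | 0.750 | 16.8 |
| 90 | 1000 | 11.11 | 11.1% | 0.741 | 16.6 |
| 100 | 1000 | 10.00 | 0 | 0.667 | 15 |

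The excess shrinks to zero towards the top of each band but stays positive: 600/59.9 = 10.02 and 1000/99.9 = 10.01 mg/kg. On a 0.01 kg grid from 30 to 99.99 kg, every weight gives more than 10 mg/kg. Above 100 kg the dose falls below label (1000/110 = 9.09).

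**Step 3: the protocol's rate.** 10/15 = 0.667, so the stated maximum comes from the label. It does not come from the table directly above it.

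**Step 4: how typical the excess is.** Spread evenly over 50-100 kg, the mean is 10.71 mg/kg, 7.1% above label. The protocol gives no weight distribution. Assuming normal weights cut off at 40 kg, with mean 75, 80 or 85 kg and SD 15 or 20 kg:

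- mean delivered dose over the whole arm: 10.34-10.72 mg/kg (3.4-7.2% above label, including patients over 100 kg who get less than label);
- share of the arm above 10 mg/kg: 77-95%;
- share above 11 mg/kg: 17-28%.

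**Step 5: how many patients.** Section 4.1 puts 10 patients in the top arm during burn-in. Five later blocks of 50, each with 13 controls, leave 5 x 37 = 185 active places, so the arm could hold at most 195. That ceiling requires adaptive randomization to send every later active place to this arm.

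**Step 6: are the arms still distinct?** From 50 to 100 kg the delivered ranges are 3-3.6, 5-6, 7-8.4 and 10-12 mg/kg. They do not overlap.

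**The case against.** The sentence in Section 4.3 can be read as describing arm labels, and the labels do lie within 2.5-10 mg/kg. The protocol does not say whether phase 1 was itself dosed in bands, or what milligram amounts were given. It refers to the Investigator's Brochure, which is not at hand, for further detail. So exposure beyond what was actually tested is not proved to the full percentages above. The largest figures are also tails: under the assumed weights only 0.2-2.8% of patients fall below 45 kg and 0.8-6.8% exceed 12 mg/kg. Running the infusion a few minutes longer removes the rate problem from 50 kg up. The rule "No dose reductions are allowed in this study" stands in Section 7.1 on discontinuing the infusion, so it says little about how the starting dose is set. Dose-escalation burn-in, intensive care for the first 24 hours, the safety stopping rule and the data and safety monitoring board all limit harm.

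The points on the size of the tails, the infusion time and Section 7.1 stand and temper the finding. The reading by label does not rescue the text: a safety justification has to hold for the dose patients receive, and Section 6.1.2 makes that the Table 2 dose. Without anything in the protocol to the contrary, 10 mg/kg is the only comparator it offers. Monitoring limits the consequences but does not make the stated range correct.

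**Conclusion.** The protocol contradicts itself. Following Table 2 correctly gives every patient under 100 kg in the top arm more than the highest dose reported from phase 1: up to 11.67 mg/kg from 60 kg upwards, and without bound below 60 kg. This rests on division of the protocol's own figures. Only the estimates for the arm as a whole (mean 10.3-10.7 mg/kg, 77-95% of patients above 10 mg/kg) depend on the assumed weights.

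For most patients the excess is modest, and it does not disturb the order of the arms, their separation from 50 to 100 kg, or the comparison with placebo. The fault is a false safety limit, plus a maximum rate that is exceeded unless the infusion runs to about 17-18 minutes (50 kg and over). It should be corrected.

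**What to change.** **Preferred.** Replace Table 2 by: dose (mg) = label x the smaller of actual weight and 100 kg, made up to 200 ml as now. The top arm then never exceeds 10.0 mg/kg, or 10/15 = 0.667 mg/kg/min over 15 minutes, and nobody under 100 kg is systematically underdosed. From 100 kg up, doses stay at 300, 500, 700 and 1000 mg. Cap the weight and not only the milligrams: with a 1000 mg cap alone, the 7 and 10 mg/kg arms would receive the same dose from 1000/7 = 143 kg. A printed look-up in 1 kg steps, with weight rounded down, keeps a table on hand and costs at most 1/50 = 2% of dose from 50 kg.

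**If Table 2 must stay.**

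1. Dose by label x actual weight below 60 kg, so that the top-arm maximum is 11.67 mg/kg.
2. State in Section 4.3 that the top arm delivers 10.0-11.7 mg/kg from 60 to 100 kg, above the reported phase 1 maximum, and justify it.
3. Give the maximum rate in Section 6.1.2 as 0.78 mg/kg/min, or infuse over at least 17.5 minutes (11.67/17.5 = 0.667).

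If the row under 60 kg is also kept, Section 4.3 must say that the top-arm dose there is 600 mg divided by weight, with no upper bound unless a minimum weight or mg/kg cap is set.

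**Cost.** One table is amended in the protocol and the Pharmacy Manual, and pharmacists are retrained. A longer look-up is somewhat more open to error than five rows, and drug must be started within 90 minutes of qualifying perfusion imaging. No arm needs more 100 mg vials than under Table 2, and sample size, randomization and blinding do not change. If patients have already been dosed, each label would cover two dosing rules, differing by about 7% on average below 100 kg, against steps of 40-67% between arms (5/3, 7/5, 10/7). Weight and milligrams given should then be recorded and delivered mg/kg reported.
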